11.2 Sample Size

Based on previous studies, it is expected that at one year approximately 5% of the participants in the standard care group will have achieved $\geq 15\%$ weight loss (likely range: 3%-5%) [5, 7]. An achievable target for $\geq 15\%$ weight loss at one year in the intervention group is 16% (likely range: 14%-20%) [5,7]. Based on these proportions, 25% drop out, 5% alpha and a 2:1 randomisation ratio with the higher proportion of participants being randomised to the intervention group, we would need to recruit 392 participants (261 intervention group; 131 standard care) to have 80% power to detect a significant difference between the groups at one year. With 261 participants randomised to the intervention group, and based on 16% achieving $\geq 15\%$ weight loss at 12 months, an estimated 40 participants in the intervention group will be eligible for the responder analyses. All 131 participants in the standard care group will be eligible for the responder analyses.

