2.2 Secondary Endpoints

2.2.1 Definition and Derivation of Secondary Endpoints

Endpoint	Time point (weeks)	Endpoint derivation
Anthropometric endpoint		
Absolute change in weight (kg) from baseline	16, 32, 52, 104	Follow-up weight – baseline weight
Relative change in weight (%) from baseline	16, 32, 52, 104	(Baseline weight – follow-up weight)/baseline weight * 100
Weight loss of $\geq 5\%$, $\geq 10\%$ and $\geq 15\%$	16, 32, 52, 104	Binary indicator of 1 if relative change in weight from baseline is $\geq 5\%$ loss (or $\geq 10\%$ or $\geq 15\%$, respectively), 0 otherwise
Maintenance of weight loss of $\geq 15\%$ among those who lost $\geq 15\%$ at 52 weeks	104	Binary indicator of 1 if relative change in weight from baseline is $\geq 15\%$ loss, 0 otherwise, only calculated for those who lost $\geq 15\%$ of baseline weight at 52 weeks.
Absolute change in BMI (kg/m^2) from baseline	52, 104	Follow-up BMI – baseline BMI
Absolute change in waist circumference (cm) from baseline	52, 104	Follow-up waist circumference – baseline waist circumference
Obesity-related co-morbidities and their treatments (General)		
Score on King's College Obesity Staging System assessment	52, 104	Scored as per Staging System (Appendix 1) as Stage 0 (normal health), 1 (at risk of disease), 2 (established disease), 3 (advanced disease) with baseline values also presented
Quality of life (EQ5D) – Descriptive System	52, 104	Scored as per https://www.unmc.edu/centric/_documents/EQ-5D-5L.pdf with change from baseline value analysed separately for each dimension
Quality of life (EQ5D) – Visual Analogue Scale	52, 104	Scored as per https://www.unmc.edu/centric/_documents/EQ-5D-5L.pdf with change from baseline value analysed
Impact of Weight on Quality of Life-Lite (IWQOL-Lite)	52, 104	Transformed total score on scale of 0-100 scored as per https://www.qualityoflifeconsulting.com/iwgol-lite.html with change from baseline

		value analysed
Patient Health Questionnaire-9 (PHQ-9)	52, 104	Scored as per Appendix 2 as minimal depression, mild depression, moderate depression, moderately severe depression, severe depression with baseline values also presented
Patient Health Questionnaire-9 (PHQ-9)	52, 104	Total score generated as per Appendix 2 with change from baseline analysed
Obesity-related co-morbidities and their treatments (Obstructive Sleep Apnoea; OSA)		

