4.6 Statistical Significance

All statistical tests, p-values, and confidence intervals will be two-sided. Statistical significance will be assessed at the 5% level for main effects. No interaction analyses are planned, however if post-hoc interaction effects are tested then these will be assessed at the 10% level.

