5.5 Secondary Outcome Analyses

5.5.1 Primary Analysis of Secondary Outcomes

Secondary anthropometric outcomes will be analysed in a similar way to the primary analysis. These outcomes will be summarised overall and by treatment group.

Categorial outcomes will be summarised using count and percentage. Continuous outcomes will be summarised using mean, standard deviation, median, range, and interquartile range. Binary anthropometric outcomes will be compared between the two treatment arms using logistic regression models with the anthropometric outcome as the outcome and randomisation group and the stratification factors (site, baseline BMI) as covariates. The adjusted odds ratio will be presented along with 95% confidence interval and p-value comparing the two treatment arms. Continuous anthropometric outcomes will be compared using linear regression models with the anthropometric outcome as the outcome and randomisation group and the stratification factors (site, BMI) as covariates. The adjusted mean difference will be estimated along with 95% confidence interval and p-value comparing the two treatment arms. If continuous outcomes are non-normally distributed then they will be transformed or a more suitable regression model will be selected.

No formal statistical testing will take place for the other secondary outcomes due to the large amount of secondary outcomes and to reduce multiple testing. Instead, descriptive analyses will be performed to explore potential patterns in improvements. This will apply to the outcomes relating to obesity-related co-morbidities, referrals to Tier 4 services, treatment satisfaction, treatment compliance, and physical activity. Categorial outcomes will be summarised using count and percentage. Continuous outcomes will be summarised using mean, standard deviation, median, range, and interquartile range. Where it makes sense to do so, for continuous variables the baseline, follow-up, and change values will all be summarised; some outcomes can only be defined at follow-up and so this will not apply to those outcomes.

In all analyses, participants will be analysed in the group to which they were randomised at baseline. Only the complete cases population will be used for the secondary outcomes to reduce the number of models being fitted. Participants who have undergone bariatric surgery during the period of the study will be excluded from these analyses if their bariatric surgery took place before the analysed time-point.

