5.5.3 Sensitivity Analyses

No sensitivity analyses are planned.

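### Separate complete-case regressions for weight change leave earlier weights unused, so response-linked dropout that differs by arm could bias the later weight differences in either direction

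*SAP*

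**What the plan says.** - **Outcomes.** SAP 2.2.1 lists "Absolute change in weight (kg) from baseline" and the relative change at weeks 16, 32, 52 and 104.
- **Model.** SAP 5.5.1 uses linear regression with randomised group, site and BMI group as covariates. Template table 16.9 has a separate adjusted difference and p-value for each visit. There is no repeated-measures term, and no earlier weight is a covariate.
- **Population.** "Only the complete cases population will be used for the secondary outcomes to reduce the number of models being fitted" (SAP 5.5.1). SAP 3.3.1 defines complete cases outcome by outcome, so a missing week-52 weight removes the participant from the week-52 model whatever was recorded before.
- **Missing data.** SAP 4.2 gives an imputation rule for the binary primary outcome only. For secondary outcomes SAP 5.5.3 states: "No sensitivity analyses are planned". The responder analysis in 5.5.2 restricts the intervention arm further and does not address missing data.
- **Stopping rules.** Protocol 6.2 stops the study drug at weeks 16, 32 and 52 for intervention participants below a weight-loss target. Controls have no counterpart.
- **Interim data.** Weight is scheduled at every visit in Protocol Appendix 3, and weeks 16 and 32 are not among the visits made optional in Protocol 8.4.

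**The concern.** Early weight loss decides what a participant receives in one arm and not in the other. Anyone who loses the drug after a poor early response might also stop attending, and a disappointed control in an open-label trial might do the same. If such dropout differs by arm, those weighed at week 52 or 104 are a selected set, selected differently in each arm. The early weights that would reveal and correct this are already collected, but the later-visit models do not use them.

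The anthropometric outcomes are the only secondary outcomes with formal tests, so their differences and p-values will be read as evidence. A reader could not tell from the report whether a week-104 difference was too large or too small.

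**Working it through.** **The plan's own figure.** The documents give no standard deviation, correlation or power for continuous weight change. Their only sample size is for the binary primary outcome: "392 participants (261 intervention group; 131 standard care) to have 80% power", with "25% drop out, 5% alpha and a 2:1 randomisation ratio".
- With 5% v 16%, two-sided, the pooled proportion is (0.05 + 2 × 0.16)/3 = 0.1233.
- Controls needed = [1.960 √(1.5 × 0.1233 × 0.8767) + 0.842 √(0.05 × 0.95 + 0.16 × 0.84/2)]² / 0.11² = 95.4, so 96.
- Total 288; 288/0.75 = 384, which is 2% below 392. Power at 98/196 evaluable is 81.2%.

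The figure reproduces. What matters here is the dropout it allows: 0.25 × 392 = 98 participants without a week-52 result.

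**Illustration at week 52. All inputs are assumed; loss counts as positive, in percentage points.**
- Week-16 loss: mean 3 (control), 6 (intervention), SD 4.
- Week-52 loss: mean 4 and 8, SD 8, so the true difference is 4.0.
- Correlation 0.7. Regression slope β = 0.7 × 8/4 = 1.4.
- Response-linked dropout: 40% if the week-16 loss is below 5, 12% otherwise. Random dropout: 25%.

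For an arm with week-16 mean μ, let z = (5 − μ)/4, P = Φ(z) and A = μP − 4φ(z), the part of the mean contributed by those below 5. Among those retained, the week-16 mean is [0.60A + 0.88(μ − A)] / [0.60P + 0.88(1 − P)]. Its excess over μ, times β, is the shift in the week-52 complete-case mean.
- Intervention: P = 0.4013, A = 0.861. Retained mean = (0.60 × 0.861 + 0.88 × 5.139)/0.7676 = 6.564. Shift = 1.4 × 0.564 = 0.79.
- Control: P = 0.6915, A = 0.666. Retained mean = (0.60 × 0.666 + 0.88 × 2.334)/0.6864 = 3.574. Shift = 1.4 × 0.574 = 0.80.

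| Dropout linked to response in | Complete cases | Using week-16 weight |
|---|---|---|
| Intervention only | 4.0 + 0.79 = 4.79 | about 4.0 |
| Control only | 4.0 − 0.80 = 3.20 | about 4.0 |
| Both arms, same rule | 4.0 + 0.79 − 0.80 = 3.99 | about 4.0 |
| Neither | 4.0 | about 4.0 |

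Simulated trials of 131 and 261 agree with the table. In the first scenario the standard error falls from 0.98 to 0.92, or 1 − 0.92/0.98 = 6%. Weaker contrasts give less bias: control 31%/12% with intervention 40%/12%, or random control dropout with intervention 30%/20%, each give about 4.3.

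**Second simulation, carried to week 104.** Assumed differences are 3.0 points at week 52 and 2.0 at week 104, SDs 8 and 9, dropout 25% and 35%.

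| Dropout pattern | Error in benefit, week 52 | Week 104 |
|---|---|---|
| Unrelated to weight, or equal link and equal rates in both arms | about 0 | about 0 |
| Linked in intervention only | overstated 0.8 to 1.45 | overstated 1.2 to 2.1 |
| Linked in control only (stronger link) | understated 1.5 | understated 2.1 |
| One common model, so more controls leave | understated 0.2 to 0.7 | understated 0.3 to 0.75 |

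A likelihood analysis using the earlier weights stayed within about 0.05 points of the truth throughout. Its week-52 standard error was 0.90 against 0.98, 8% smaller. The last row shows that the cancellation under a shared rule in the first table is not guaranteed.

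**The case against.** **No bias is shown.** A reader might infer that the planned analysis overstates the benefit, by 20% in the first scenario. The documents do not support that. Nothing in them says dropout follows early response, or does so in one arm only. Stopping the drug is not leaving the study: Protocol 6.2 keeps these participants in standard care and in the Clinical Review Visits. The 20% belongs to one chosen pattern; others give zero or the opposite sign. This stands, and limits the point to a possible bias of unknown direction.

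**The stated reason.** A reader might also argue that reducing the number of models favours one repeated-measures model over four regressions. The sentence most naturally explains why secondary outcomes are not repeated in the ITT and per-protocol populations; it does not concern time points. The fix also keeps the regressions, so it does not reduce the count. That argument should not be used.

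**Mitigation.** The plan works to obtain week-52 weights: a ±3-month window, record weights within ±12 weeks (SAP 1.3), home weights (Protocol 8.10) and a payment tied to having the weight (Protocol 8.3.2). SAP 5.3 compares baseline characteristics of those with and without primary-outcome data. These measures stand, but mainly for week 52; week 104 keeps a ±14-day window. They reduce missingness without allowing for what remains.

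**Surgery.** SAP 5.5.1 excludes participants at visits after bariatric surgery. In a likelihood model, weights set to missing are implicitly predicted from the pre-surgery course, which changes the quantity estimated. This stands and has to be stated in the plan.

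**Conclusion.** The point holds as a conditional one. The later-visit models leave known earlier weights unused, and nothing in the plan tests what that does to the continuous weight results. If dropout depends on early response differently by arm, the week-52 difference could be off by about 0.8 points in either direction on an assumed 4.0, and by up to about 1.5 under the second set of assumptions. At week 104 the range reached about ±2.1 on an assumed 2.0. If dropout is unrelated to weight, there is no bias and only some precision is lost.

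These sizes rest on assumed means, SDs, correlations and dropout rules, and on data being missing at random given the observed weights. The week-16 comparison gains little, because the proposed model contains no earlier visit. The primary outcome is not affected. This is an improvement that should be made; it does not show that the reported results will be wrong.

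**What to change.** In SAP 5.5.1, analyse absolute weight change and relative weight change each with one mixed model for repeated measures over weeks 16, 32, 52 and 104. Include arm by visit, site, BMI group and baseline weight by visit, with an unstructured covariance, and report the adjusted difference at each visit. Keep the planned complete-case regressions and list them in SAP 5.5.3 as sensitivity analysis.

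State two things in the text:
- The model assumes missing at random given the observed weights. This is weaker than what the complete-case regressions need, but it is still an assumption.
- Setting weights after bariatric surgery to missing in this model targets weight as if surgery had not occurred, which differs from the present exclusion.

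The cost is SAP wording and one extra model for each of the two outcomes. Baseline weight by visit is an addition to the planned covariates and should be recorded as such in SAP 5.8. No new data are needed. The SAP is marked as a draft and provides for amendment and sign-off before database lock.

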6. STUDY DESIGN

6.1 Summary of Trial Design

[figure not shown]
A 26 month, parallel, two group, open-label, real-world, RCT design for patients with severe and complex obesity who are referred to a Tier 3 obesity service (including patients who are referred to a Tier 3 service as part of the bariatric surgery pathway). The total duration of participation will be 104 weeks (+/-2 weeks).

The first 52 weeks of the study (after randomisation) will determine whether using the targeted prescribing pathway in a Tier 3 setting will result in more participants attaining $\geq 15\%$ weight loss compared with standard care. The second 52 weeks of the study will assess whether patients who lose $\geq 15\%$ of their baseline weight by the first 52 weeks are more likely to maintain $\geq 15\%$ weight loss for another 52 weeks in the targeted prescribing pathway compared with standard care. Further, budget impact, cost-effectiveness, improvement in obesity-related co-morbidities, complementary aspects of safety, effectiveness, adherence, and treatment satisfaction of both treatment groups will be assessed and compared (see Section 6.4.2).

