- Proportion of participants with hypertension (defined as patients on antihypertensive medications or systolic blood pressure >140mmHg)
- Dose, class of medication, and number of agents for hypertension

Obesity-related co-morbidities and their treatments (Dyslipidaemia)

- Lipids
- Dose, class of medication, and number of agents for dyslipidaemia

Number of participants referred for other obesity intervention

- Number of participants referred to Tier 4 for bariatric surgery over the 104 weeks study period

Direct healthcare cost

- Frequency and cost of contact with General Practitioner (GP) (type and duration of contact will be recorded to enable use of Tariff prices from <http://www.pssru.ac.uk/project-pages/unit-costs/2016/index.php?file=full> to calculate accurate costings – accessed 21/07/2017)
- Frequency and cost of contact with Healthcare Professionals (HCP) (type and duration of contact will be recorded to enable use of Tariff prices from <http://www.pssru.ac.uk/project-pages/unit-costs/2016/index.php?file=full> to calculate accurate costings)
- Frequency of admissions, length of stay and cost of admissions to the hospital
- Frequency and cost of outpatient appointments with the hospital
- Prescription medication costs
- Health Service and Resources Use Questionnaire (HSRUQ)

Budget impact of Tier 3 service

- Cost of the proposed LIRA 3mg (as per protocol - e.g. actual dose taken = number of days taking study drug x daily cost of drug, or cost of total amount of study drug used)
- Cost of visits to clinician for assessment and medication prescription during Tier 3 programme
- Cost of visits to dietitian during Tier 3 programme
- Cost of visits to psychologist during Tier 3 programme
- Cost of exercise physiologist/physiotherapist during Tier 3 programme (if applicable)
- Cost of Multidisciplinary Team (MDT) discussion in Tier 3 service
- Cost of blood tests in Tier 3 service
- Cost of consumables and goods
- Cost of referral into Tier 4

Estimated cost-effectiveness of treatment over 2 years

- Length of treatment with LIRA 3mg
- Daily dose of LIRA 3mg (based on actual doses taken)

Safety/adverse events

- Gastrointestinal symptoms (nausea, vomiting)
- Overall hypoglycaemia rate
- Overall AE/SAE rate
- Rates of severe hypoglycaemia
- Heart rate
- Blood pressure

(See Section 10.4 for definitions of hypoglycaemia)

Treatment satisfaction

- Treatment Satisfaction Questionnaire for Medication (TSQM)

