Secondary outcomes measured at 52 weeks and 104 weeks will be analysed in a similar way, with binary outcomes compared using logistic regression models and summarised using proportion (95% confidence interval), and continuous outcomes compared using linear regression models and summarised using mean (95% confidence interval). If continuous outcomes are non-normally distributed then they will be transformed or a more suitable regression model will be selected. In all analyses, participants will be analysed in the group to which they were randomised at baseline. Only the complete cases population will be used for the secondary outcomes to reduce the number of models being fitted. Participants who have undergone bariatric surgery during the period of the study will be excluded from these analyses. Data on treatment adherence, safety (including adverse events), and treatment satisfaction will be summarised and tabulated.

As additional secondary analyses, we will perform a responder analysis which will repeat the analyses of the secondary outcomes with the intervention group restricted to those participants who responded to the targeted prescribing pathway (i.e. had achieved $\geq 15\%$ weight loss at 52 weeks after randomisation). The purpose of these analyses is to compare the outcomes of “early and good” responders to the targeted prescribing pathway with those who received standard care only. Therefore, all participants randomised to the standard care group will also be included in these responder analyses.

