Proportion of those with diabetes at baseline with HbA1C<6.5%	52, 104	From HbA1c measurement, a binary indicator will be derived, being 1 if participant achieves the target and 0 if they do not.
Change in Albumin-Creatinine Ratio (ACR; mg/mmol) from baseline for participants with diabetes, prediabetes, or hypertension	52, 104	Follow-up ACR – baseline ACR, only for participants defined as having diabetes, prediabetes, or hypertension
Obesity-related co-morbidities and their treatments (Hypertension)		

Systolic blood pressure (mmHg)^b	52, 104	Follow-up systolic blood pressure – baseline systolic blood pressure
Diastolic blood pressure (mmHg)^b	52, 104	Follow-up diastolic blood pressure – baseline diastolic blood pressure
Hypertension	52, 104	Binary indicator of 1 if participant is on antihypertensive medications or systolic blood pressure > 140 mmHg ^c , 0 otherwise with baseline values also presented
Number of agents for hypertension	52, 104	Change from baseline in total number of medications taken for hypertension defined as medications in any of the following classes: ACE-inhibitors, calcium channel blockers, thiazide diuretics, alpha-blockers, and beta-blockers.
Obesity-related co-morbidities and their treatments (Dyslipidaemia)		
LDL cholesterol (mmol/L)	52, 104	Follow-up LDL cholesterol – baseline LDL cholesterol
HDL cholesterol (mmol/L)	52, 104	Follow-up HDL cholesterol – baseline HDL cholesterol
Total cholesterol (mmol/L)	52, 104	Follow-up total cholesterol – baseline total cholesterol
Triglycerides (mmol/L)	52, 104	Follow-up triglycerides – baseline triglycerides
Number of agents for dyslipidaemia	52, 104	Change from baseline in total number of medications taken for dyslipidaemia defined as medications in any of the following classes: statins, fibrates, and ezetimibe.
Number of participants referred for other obesity intervention		
Referred to Tier 4 for bariatric surgery	104	Binary indicator of 1 if participant was referred to Tier 4 for bariatric surgery over 104 week period, 0 otherwise
Treatment satisfaction		
Treatment	Satisfaction	Questionnaire for Medication (TSQM)
	52, 104	Change from baseline in TSQM scale score. Scored as per version II (detailed in Appendix B on vhe.066.fm (iqvia.com)).
Safety/adverse events		
Gastrointestinal symptoms	52, 104	Binary indicator of 1 if participant experienced any nausea or vomiting in study up until the time point of interest (captured in the expected AEs), 0 otherwise

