3.3.1 Complete Cases Population

The complete cases population is defined as all randomised participants who have data available for the outcome being analysed, according to the study group to which they were randomised at baseline. Participants who had bariatric surgery during the study period will be only be included at time-points prior to their bariatric surgery. They will be excluded from time-points after their bariatric surgery.

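### Tier 4 referral is reported only at week 104, yet participants operated on before week 104 are excluded, so people who were referred and had surgery in the study are not counted

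*SAP*

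**What the plan says.** The protocol (6.4.2) lists the outcome as "Number of participants referred to Tier 4 for bariatric surgery over the 104 weeks study period". SAP 2.2.1 turns it into a per-participant variable with 104 weeks as its only time-point: "Binary indicator of 1 if participant was referred to Tier 4 for bariatric surgery over 104 week period, 0 otherwise". The table template in SAP 16.10 has one block for it, by 104 weeks.

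SAP 5.5.1 names Tier 4 referrals among the outcomes to be summarised descriptively: "No formal statistical testing will take place for the other secondary outcomes". The same section fixes the population, "Only the complete cases population will be used for the secondary outcomes", and adds that participants who had bariatric surgery "will be excluded from these analyses if their bariatric surgery took place before the analysed time-point".

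The definition of the complete cases population in SAP 3.3.1 carries the same rule for operated participants: "They will be excluded from time-points after their bariatric surgery". Protocol 11.1 is stricter and excludes them from the secondary outcome analyses regardless of when surgery took place: "Participants who have undergone bariatric surgery during the period of the study will be excluded from these analyses". SAP 5.8 records the change from the protocol's rule to the time-dependent one. None of these sections makes an exception for the referral outcome.

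**The concern.** The exclusion was written for weight. Protocol 6.2 and 11.1 justify it by the large weight loss after surgery and by the expectation that more controls than intervention participants will have surgery. That reasoning does not carry over to the question of whether a referral was made. Tier 4 is bariatric surgery (Protocol 6.2), so here the rule removes the participants who went furthest along the pathway that the outcome is meant to count.

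At stake is secondary objective 2, the comparison of referral rates to other obesity interventions. Those who were referred and operated on within two years disappear from the result, while those referred and still waiting at week 104 are kept. Because the protocol expects surgery to be unbalanced, the number removed is expected to differ between arms, so the contrast as well as the level may be distorted.

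**Working it through.** **Does the rule reach this outcome?**

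1. The only time-point is week 104 (SAP 2.2.1; one block in SAP 16.10).
2. The outcome is one of the secondary outcomes governed by SAP 5.5.1, which names it.
3. The only population allowed for it is complete cases (SAP 5.5.1).
4. That population drops a participant from time-points after surgery (SAP 3.3.1). Surgery at any time before week 104 therefore removes the participant from the single time-point.
5. SAP 5.8 relaxes the protocol's blanket exclusion only for time-points before surgery. This outcome has no earlier time-point, so the relaxation does not help it.

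**Effect on the percentage.** The plan gives no referral rate, surgery rate or time from referral to surgery, so there is no figure of its own to reproduce. Let *r* be the true proportion referred in an arm and *f* the share of those referred who are operated on before week 104. Assume for now that everyone operated on had an in-study referral. Then

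reported proportion = *r*(1 − *f*) / (1 − *rf*),

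which is below *r* whenever *f* > 0 and *r* < 1. The reported odds are *r*(1 − *f*)/(1 − *r*), so if *f* is the same in both arms the odds ratio is unchanged, although both percentages and their difference shrink.

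**Illustration, all inputs assumed:** *r* = 15% in control and 8% in intervention. The true difference is 7.0 points and the true odds ratio is (0.15/0.85)/(0.08/0.92) = 2.03. Worked line for *f* = 0.50 in both arms: control 0.15 × 0.5/(1 − 0.075) = 0.075/0.925 = 8.1%; intervention 0.08 × 0.5/(1 − 0.04) = 0.04/0.96 = 4.2%.

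| *f* control | *f* intervention | Reported control | Reported intervention | Difference (points) | Odds ratio |
|---|---|---|---|---|---|
| 10% | 10% | 13.7% | 7.3% | 6.4 | 2.03 |
| 25% | 25% | 11.7% | 6.1% | 5.6 | 2.03 |
| 50% | 50% | 8.1% | 4.2% | 3.9 | 2.03 |
| 70% | 70% | 5.0% | 2.5% | 2.5 | 2.03 |
| 30% | 50% | 11.0% | 4.2% | 6.8 | 2.84 |
| 50% | 30% | 8.1% | 5.7% | 2.4 | 1.45 |
| 20% | 50% | 12.4% | 4.2% | 8.2 | 3.25 |

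**The same effect in whole participants,** using the planned arm sizes (131 control, 261 intervention; Protocol 11.2), full follow-up and a second set of assumed rates. With 26 referred in each arm, the true figures are 26/131 = 19.8% and 26/261 = 10.0%, a difference of 9.8 points. If 13 of the 26 in each arm are operated on before week 104, the plan reports 13/118 = 11.0% and 13/248 = 5.2%, a difference of 5.8 points.

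**A difference can also appear where there is none.** With 26/131 and 52/261 referred (19.8% and 19.9%), and 13 operated on in each arm (50% of referred controls, 25% of referred intervention participants), the plan reports 13/118 = 11.0% and 39/248 = 15.7%. This is a difference of −4.7 points against a true −0.1.

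**The case against.** Four points can be put on the other side.

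- **The text may not intend this.** The SAP 16.10 template has a row for missing values, which would always be empty under a strict complete cases rule. SAP 3.1 says data from all randomised participants will be used. The reason given in SAP 5.5.1 for using complete cases is to limit the number of models, and no model is fitted here. These are fair hints that a wider denominator was in mind. They do not override the explicit exclusion, which is stated twice, and a programmer following the text would drop these participants.
- **The percentage need not fall.** Some participants enter Tier 3 through the surgical pathway (Protocol 6.1: "including patients who are referred to a Tier 3 service as part of the bariatric surgery pathway") and could be operated on without a recorded in-study referral. If a share *s* of the arm does so, the reported proportion is *r*(1 − *f*)/(1 − *rf* − *s*), which exceeds *r* when *s* > *f*(1 − *r*). With *r* = 0.15, *f* = 0.10 and *s* = 0.10, all assumed, it is 0.135/0.885 = 15.3%. This stands. It qualifies the direction of the error but not its existence.
- **The size is assumed throughout.** This also stands. No conversion rate can be taken from the documents, and the scenarios include one in which the gap widens.
- **The consequence is limited.** The outcome is untested, and the disposition table (SAP 16.1) shows how many participants had surgery in each arm. That lets a reader see how many could be affected, but it counts operations, not referrals, and does not put anyone back into the referral percentage.

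**Conclusion.** The concern holds. As written, the plan removes participants who met the Tier 4 referral outcome because they went on to have the surgery they were referred for. The reported percentage falls in any arm where this occurs, unless enough participants are operated on without an in-study referral to offset it. If referral is more common in control and conversion to surgery is similar or higher there, the absolute difference between arms is attenuated. In the 15% v 8% illustration, with equal conversion of 10% to 70%, the 7.0-point difference becomes 6.4 down to 2.5 points. With the unequal conversions tried it ranges from 2.4 to 8.2 points. These rates are assumptions, and the documents fix neither size nor direction. The effect is confined to a descriptive secondary outcome: no p-value and no primary result is touched. It should still be corrected, because it misreports a named secondary objective.

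**What to change.** Add one sentence to SAP 5.5.1 stating that the bariatric surgery exclusion does not apply to the Tier 4 referral outcome. Specify that it is summarised by randomised arm in all randomised participants with referral status recorded, with operated participants kept in numerator and denominator according to their recorded in-study referral. Report missing referral status as missing. Do not simply point to the ITT population, since SAP 3.3.2 says missing outcomes there are imputed. Do not count surgery as a referral automatically, because of participants who entered through the surgical pathway.

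Log the change in SAP 5.8, where departures from the protocol are already recorded. A matching sentence in Protocol 11.1 would keep the documents aligned but is not essential: the SAP is dated 01/08/2022, after the study end date of 30/06/2022 in the protocol's amendment history.

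The cost is small. Tier 4 referrals are already a collected variable (Protocol Table 1), so no new data are needed. The SAP copy is marked as a draft, and its introduction allows amendment before database lock.
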